#### **13.4 Heart Rate Variability Data**

Following a 24-hour recording, a study team member will collect the Actiheart monitor from the patient (either in clinic or while in the hospital). De-identified data from the device will be uploaded into the Actiheart software (CamnTech, Inc), which will be installed on one computer located in the locked office of the study PI. Data will then be transferred to the above mentioned encrypted RedCap database.

#### **13.5 Data Collection Procedures/ Internal Site Monitoring plan**

The coordinating center will be responsible for systematic data collection, quality control, and data-management procedures including: (1) oversight of ongoing data collection; (2) rigorous training and ongoing monitoring of adherence to protocols; (3) regular review of questionnaire response rates and missing items to identify and correct problems; (4) verification of all data through computerized data entry systems restricting invalid/out-of-range responses; (5) at minimum monthly meetings and progress reports to provide feedback to study staff concerning difficulties and follow-up to ensure problems are resolved quickly; and, (6) yearly on-site monitoring of participating sites

**13.5.1 Survey data.** To optimize collection, all participant surveys will be available by paper or online via the REDCap system, a secure HIPAA-compliant, high-quality data collection tool. Surveys may also be completed in person with a study team member. The rationale for offering both paper-pencil and electronic versions is based on our prior experience where participants preferred the former, which in turn facilitated more complete data collection. To ensure primary outcome data, we will offer an interview and/or abbreviated survey with only the PedsQL for those who do not complete all assessments or who request to drop out or who are too ill to complete the entire survey. To ensure data quality, a RA will review RPCA surveys within 72 hours of their completion for missing fields and call participants sites to clarify and query/complete individual missing items verbally.

**13.5.2 Medical record data.** RA's will collect and upload CRF data monthly for both the run in and RCT 3 months post baseline. CRF data will also be collected at 6-, 9-, and 12-months for the RCT only. To ensure reliability and validity of abstracted medical record data, we will use our current methods for training and quality, including guided practice abstraction and independent abstraction with reconciliation by a trainer. A 10% random sample will be dual abstracted. A RA assignment will monitor and reconcile case report forms with RedCap data once monthly.

#### **13.5.3 Heart Rate Variability Monitors**

Staff investigators and RA's will be trained on recognizing adequate signal acquisition on the Actiheart monitors when the patient initially has the device placed. If there is suboptimal recording identified, the team member placing the device will be able to recognize in real time and make appropriate adjustments to the equipment based on Actiheart user manual suggestions.

## 13.6 Safety and Compliance Monitoring

This is a small multisite clinical trial of a supportive care intervention with no more than a minor increase over minimal risk and the prospect of direct benefit. As such, data monitoring will be primarily carried out by the Lead RA at the coordinating site (SCH) and a small, external Data Safety Monitoring Committee (DSMC).

**13.6.1 Data and Safety Monitoring Plan.** Safety monitoring will be the responsibility of a 4-member Data Safety and Monitoring Committee (DSMC) composed of professionals across the country representing different disciplines and expertise (see table below). All members are independent of the protocol. The committee will be convened at the beginning of the study and then twice annually via conference calls, to provide input and guidance on the study evaluation and intervention protocols, including quality assurance and safety issues related to the protocols, as well as data handling activities. As above, in the event of an unanticipated patient death, the committee may convene an ad-hoc session and/or suspend the study to assess patient risk and/or necessary revisions to the protocol.

### 13.6.2 Data and Safety Monitoring Committee

Member Name, Title	Discipline	Research Expertise
[name] (Associate Professor, Pediatrics University of Texas, San Antonio)	Pediatric Psychology	Behavioral Science, Adolescent and Young Adult Oncology
[name] (Professor, Pediatrics Children's Hospital, Eastern Ontario)	Pediatric Oncology and Palliative Care	Pediatric Oncology and Palliative Care, Clinical Trial Design, Patient-Reported Outcomes
[name], MSW (Professor, Pediatrics University of Texas, Austin)	Pediatric Social Work	Psychosocial Oncology, Pediatric Palliative Care, Adolescent and Young Adult Oncology
[name], MPH (Assistant Professor, Pediatrics, Boston Children's Hospital & Dana Farber Cancer Institute)	Pediatric Oncology	Pediatric Oncology and Palliative Care, Patient-Reported Outcomes

**13.6.3 Monitoring study safety.** DSMC members will provide input and feedback to the PI and Co-investigators, via e-mail and conference calls, related to (a) accrual rate, (b) study eligibility determination issues, (c) data completion rates including conformance with informed consent requirements, (d) intervention fidelity indicators, (e) adverse events, and (f) compliance with data management procedures. The lead statistician will oversee the summarization of online data to evaluate data completeness and protocol adherence. The Lead RA will also send monthly reports summarizing recruitment and other site specific data (such as indicators of intervention delivery, occurrence of adverse events, and conformance with IRB requirements).

The committee will also receive information on questionnaire data, presented for the participants overall rather than by study group. This study will not have pre-set stopping rules, but the DSMC will have the option of requesting the data be unblinded and considering altering the study or stopping the study early. Although the full committee will meet twice-yearly, the chair will be free to assemble the full committee

at any time if the chair believes it is important. Because committee members may be located at various sites, the committee meetings may be conducted by phone.

Data safety monitoring for the intervention will focus on assuring that subjects are not experiencing any significant or unexpected distress and that they are satisfied with the intervention components; we will monitor all complaints about the study. We do not anticipate stopping the study early for efficacy or harm, but the DSMC will have the option to consider such action in the event of a highly unexpected result. The DSMC will review the draft questionnaires to be sent to subjects and review any complaints that may be received from patients, family members, clinicians, or others. We do not anticipate any external factors such as findings from ongoing trials that will affect the safety of participants or the ethics of this research study.

**13.6.4 Identification, review and report of adverse events and unanticipated problem.**

Adverse events information will be collected at all assessment points and recorded on standard forms. We will collect information on all potential types of adverse events. Consistent with NIH and the sites IRBs policies, adverse events will be promptly reported in writing to the NIH, individual IRBs, and the DSMC chair. The DSMC will modify or stop the study if any such complaints represent a legitimate concern about the study procedures or methods.

**13.6.5 Compliance with monitoring requirements.** Compliance with the monitoring plan will be ensured through the Lead RA's close supervision. The Lead RA will hold no less than monthly calls with the sites to monitor recruitment and protocol adherence. Site RAs will gather required information on an ongoing basis and send monthly written reports to Lead RA. The Lead RA will schedule yearly on-site monitoring visits as the coordinating site for data completeness and accuracy. Site RAs will assist in providing on-site monitors with appropriate access to all study related charts and databases during the visit.**13.6.6 Assessment of relevant external factors.** Given the characteristics of the intervention, it is unlikely that a breakthrough result from another study will change the course of this study.**13.6.7 Interim analysis plan.** A primary endpoint interim analysis to assess for safety and missingness will be led by the study statistician after half of the targeted sample size of participants have reached the primary endpoint. The DSMC will determine a priori stopping occurrence of serious events, including (but not limited to) stopping the study for efficacy if interim analysis is significant. For efficacy endpoint, if an effect were found, the DSMC will be presented with unblinded results (i.e. they will be able to ascertain which results correspond to the intervention arm). Based on these results, the DSMC will present recommendations to the study team regarding early stopping or continuation of the trial. There are no pre-planned stopping rules for adverse events since these are not anticipated.**14.0 Withdrawal of Subjects****14.1 Plan for Non-Responders**

Response to the intervention will be determined upon study completion (not in “real-time.”). All participants, including those on the intervention arm, will continue to receive usual care, including as-needed referrals for professional psychology services.

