**11.5.3.4 Additional analyses** will include process evaluations that include: (a) intervention fidelity; (b) satisfaction queries; and (c) mediation analyses to evaluate relationships between PRISM, family activation, and outcomes. For example, the intervention effect on parent outcomes may be mediated by parent activation. If we find a positive intervention effect on parent psychological distress, we will explore activation mediation using the counterfactual framework with indirect mediation effects computed through G-estimation and incorporating confounders of the mediator-outcome association. Finally, we will conduct a planned interim analysis for data-safety monitoring purposes when half of AYA participants have reached the primary endpoint (see Human Subjects).

**11.5.3.5 Multiple comparisons.** Multiple comparisons are a concern since we are collecting multiple measures from both patients and caregivers and are interested in several hypotheses. We minimize this problem by specifying a limited number of main hypotheses for each aim. False Discovery Rate criterion will be used to correct for multiple testing in analyses that are not pre-specified. Likewise, in manuscripts and presentations, we will report the number of tests performed and interpret results within this context.

**11.5.3.6 Considerations regarding missing data.** Effective data collection at scheduled times will be monitored and attrition minimized as described below. While our goal will be to minimize missing data, data may still be missing due to patients/families skipping individual items, omissions in medical records, lack of follow-up, medical complications, or death. We will quantify the amount of missing data, evaluate the association of participant characteristics with missing data, and minimize bias and increase efficiency in the associations of interest by applying appropriate methods to account for missing data. For example, where missing at random (MAR) is a plausible assumption, we will use multiple imputation or inverse probability weighting, depending on the statistical model being considered. For missing not at random (MNAR), we will use sensitivity analyses. In all cases, we will assess the robustness of estimates due to assumptions.

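### Section 13.6.7 allows stopping for efficacy at an interim look but states no interim significance level and no matching final alpha, so the 5% error rate of the primary test cannot be verified

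*Combined protocol and SAP*

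**What the plan says.** **The look.** Section 13.6.7 opens with "A primary endpoint interim analysis to assess for safety and missingness will be led by the study statistician", timed at half the targeted sample. Section 11.5.3.4 describes it in similar terms: "we will conduct a planned interim analysis for data-safety monitoring purposes when half of AYA participants have reached the primary endpoint (see Human Subjects". No section of this document has the title that this pointer names.

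**Efficacy stopping.** Section 13.6.7 goes on as follows: "DSMC will determine a priori stopping occurrence of serious events, including (but not limited to) stopping the study for efficacy if interim analysis is significant". If an effect is found, the committee is shown unblinded results, and then "the DSMC will present recommendations to the study team regarding early stopping or continuation of the trial". The section ends with "There are no pre-planned stopping rules for adverse events since these are not anticipated", a disclaimer that covers adverse events only.

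**Other statements on stopping.** Section 13.6.3 says "This study will not have pre-set stopping rules", although it lets the DSMC ask for unblinding and consider stopping early. Later in the same section, early stopping for efficacy or harm is said not to be anticipated, but "the DSMC will have the option to consider such action in the event of a highly unexpected result".

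**Error rate.** The title of Table 7 (section 11.3.1) gives 80% power and a 5% type I error rate. Section 11.5.2 reports 95% confidence intervals for the primary outcome with no allowance for an earlier look. Section 11.5.3.5 says "False Discovery Rate criterion will be used to correct for multiple testing in analyses that are not pre-specified". The interim analysis is planned, so that provision does not reach it.

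**The concern.** A primary-endpoint test at the halfway point that can stop the trial for efficacy is a second chance to declare success. If the final test still uses the full 5%, overall type I error exceeds 5%, and the interim threshold determines by how much. The plan names the stopping action but omits the threshold and the final level that should go with it. The only level a reader can find is 5%. Used at the interim, it would consume the whole allowance and leave nothing for the final test.

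The text also disagrees with itself about what the look is for:

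- Within 13.6.7, a look for safety and missingness carries an efficacy stop.
- A highly unexpected result (13.6.3) and a significant one (13.6.7) are different triggers.
- The absence of pre-set rules (13.6.3) sits awkwardly beside criteria fixed a priori (13.6.7).

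At stake is whether the error rate of the only primary test can be verified. A threshold chosen after unblinding would not be credible.

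**Working it through.** **Inputs.** From sections 4.1 and 11.3.1: 72 evaluable per arm (144 in total), SD 17.2, difference 8.1 points, 80% power, 5% type I error, 195 randomized, 26% attrition. From 13.6.7: one look at half the target sample. Sidedness is not stated.

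**1. Reproduce the plan's figure.** SE = 17.2 × √(2/72) = 2.867, and 8.1/2.867 = 2.826.

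- A single two-sided 5% test has 80.7% power (normal approximation) or 80.1% (noncentral t), and the detectable difference by t-test is 8.09 points. This matches the stated 8.1.
- A one-sided 5% test would detect 7.16 points, which does not match.

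The design is therefore one two-sided 5% test with no allowance for an interim look.

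**2. Information at the look.** 72/144 = 0.50. If half of the 195 randomized (about 98) have passed month 3 and 26% of them are lost, 98 × 0.74 = 72.5 are evaluable, and 72.5/144 = 0.504. If the look instead waits for 97.5 completed surveys, the fraction is 97.5/144 = 0.68.

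**3. Overall type I error.** Under the null hypothesis the interim and final statistics (Z1, Z2) are bivariate normal with correlation √0.5 = 0.707. Overall error = 1 − P(|Z1| < c1 and |Z2| < c2), where c1 and c2 are the two-sided critical values. The last column is the final level that holds 5% overall, solved numerically.

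| Interim level | Overall error, final test at 0.05 | Final level that holds 5% |
|---|---|---|
| 0.05 | 8.31% | none left |
| 0.01 | 5.46% | 0.0452 |
| 0.005 | 5.19% | 0.0481 |
| 0.003 | 5.10% | 0.0490 |
| 0.001 | 5.02% | 0.0498 |

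Simulation confirms the 8.3%. At an information fraction of 0.68, 5% at both looks gives 7.7%.

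**4. Boundaries that hold 5%, with power at 8.1 points** (72 per arm, normal approximation, half information)

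| Interim / final level | Overall error | Power |
|---|---|---|
| No interim / 0.05 | 5.00% | 80.67% |
| 0.003 / 0.049 | 5.00% | 80.52% |
| 0.0052 / 0.0480 (O'Brien-Fleming) | 5.00% | 80.37% |

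The losses are 80.67 − 80.52 = 0.15 and 80.67 − 80.37 = 0.30 percentage points.

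**The case against.** The strongest reply is that the threshold is delegated rather than forgotten. Section 13.6.7 has the DSMC fix its criteria in advance and then only recommend, which is a recognised arrangement. A charter may hold the boundary, and none is among the documents. This stands as far as it goes: an uncontrolled error rate is not proven. But the final test level belongs in the analysis plan, and nothing here requires a written boundary or links the final alpha to one.

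Second, 8.3% is the extreme case, and 13.6.3 points away from it. Under the design effect, the expected interim statistic is 2.826 × 0.707 = 2.00, so p<0.05 at the look has about a 51.5% chance. That is hardly a highly unexpected result, so a stricter threshold fits that section better. This is fair and makes 8.3% less likely. It does not exclude it, because 13.6.7 says only significant, and the one level the plan states is 5%.

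Third, the statement in 13.6.3 that there are no pre-set rules can be squared with 13.6.7 if the protocol sets none and the committee sets its own. That is a possible reading, so the wording calls for clarification rather than being a clean contradiction. The conflict inside 13.6.7, between a safety and missingness look and an efficacy stop, remains.

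Fourth, the timing is ambiguous. Section 11.5.3.4 says only half of participants, and the endpoint in section 8.1.1 includes survey completion, so a fraction of 0.68 is possible. The error at 5% for both looks is then 7.7% instead of 8.3%, which does not change the conclusion.

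**Conclusion.** The concern holds and should be fixed before the interim look. The omission is certain within these documents: an efficacy stop is named with no interim level and no matching final alpha. The consequence is conditional. With an unadjusted final 5% test, overall type I error runs from about 5.0% (interim p<0.001) to 8.3% (5% at both looks), an excess of up to 3.3 percentage points. The 8.3% assumes that a crossing leads to stopping and that the look falls at half information. All figures assume two-sided testing (inferred from the reproduced power), information proportional to evaluable participants, and no gain from baseline adjustment. If the look involves no efficacy test, there is no inflation, but 13.6.7 as written provides for one.

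**What to change.** Before any unblinded interim data are seen, amend 13.6.7 in one of two ways.

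1. **Keep efficacy stopping.** Replace the reference to a significant interim result with a stated boundary and matching final alpha that hold 5% overall. Examples are two-sided p<0.003 at the look with p<0.049 at the end, or O'Brien-Fleming 0.0052 and 0.0480, recomputed at the actual information fraction. If the DSMC is to set the boundary, say so and require it in writing, with the final alpha, before the look. Carry the final alpha into 11.5.2.
2. **Drop efficacy stopping.** Limit the look to safety and missingness.

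In either case, state that the look occurs at 72 of 144 evaluable participants, align 11.5.3.4, 13.6.3 and 13.6.7, and redirect the cross-reference in 11.5.3.4 to 13.6.7.

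The cost is wording only, with no added participants. Option 1 takes power at 8.1 points from 80.7% to 80.5% or 80.4%. Option 2 leaves it unchanged.

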## **4.0 Study-Wide Number of Subjects**

### **4.1 Number of subjects:**

*Run-In PRISM-AC development, feasibility, and acceptability testing:* We will enroll up to 30 AYAs on a “run-in” pilot trial to refine process measures in conducting the newly added 5th session that is part of PRISM-AC. This phase of the study will be conducted ONLY at Seattle Children’s Hospital. Briefly, this “run-in” is designed as a cohort study to be conducted prior to launching the RCT phase of the study at Seattle Children’s and is expected to last approximately 6-12 months.

Parent/Caregivers/spouses/significant others may participate in PRISM session 6 (family meeting called “coming together”) but are otherwise not active study participants in this phase of investigation.

*RCT phase:* The target sample size is N=144 AYA participants (72/arm). Based on our prior work and characteristics of AYAs at participating centers (**Table 3**), we estimate identifying a total of 120 eligible AYAs/12-months (300 over the 30 months of enrollment). Assuming a conservative enrollment rate of 65% (versus 78% in phase II RCT), we expect to enroll and randomize 78 AYAs/12-months (target enrollment n=195 over the 30-months of recruitment). With a conservative attrition rate of 26% (due to medical complications as seen in pilot), we expect complete data collection on 144 AYAs (72/arm). This sample size achieves 80% power to detect an increase of 8.1 in mean Total PedsQL score, the main study outcome. Parent/Caregivers will also be invited to participate in this RCT phase of investigation as additional study subjects to complete surveys and participate in the PRISM session 6. Parents will complete surveys at the same time points as the AYAs. In our prior studies including AYA-parent dyads, >90% of caregivers participated. Hence, we expect complete data from a minimum of 128 caregivers (64/arm). Only one caregiver will be invited to complete questionnaires, and will be designated at enrollment.

**Table 3. Annual number of AYAs with advanced cancer (12-25 yrs-old) who are eligible, enrolled, and evaluable at 3 months for RCT**

Site	Total	Eligible	Enrolled	Evaluable
Seattle Children's	45	35	23	17
Texas Children's	55	35	21	16
Children's Hospital, Los Angeles	55	30	21	16
Children's Hospital, University Pittsburgh Medical Center	35	20	13	9
Total/12-months	190	120	78	58
Total for 30-month recruitment period:			195	144

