### **15.0 Risks to Subjects**

The intervention (“Promoting Resilience in Stress Management”, PRISM) and our surveys may address sensitive matters in that it they patients to identify stressors and negative thoughts. Adolescent and young adult participants may be prompted to think about the threat to their life posed by their cancer/tumor. During the coming together session and/or while completing surveys, parents may be prompted to think about the threat to their child’s life by their cancer/tumor. The topics to be covered may provoke sadness, anxiety, depression, fear or doubt for AYAs and/or their parents. Any spouse, caregiver, significant other, caregiver, etc. who participates in the coming together session may be also prompted to think about the threat to the AYA’s life posed by their cancer/tumor and these topics may provoke sadness, anxiety, depression, fear or doubt for AYAs and/or their parents.

Administrators of the intervention will be trained to inform the patient’s primary social work and/or medical teams if the patient and/or parents/guardians/spouses/significant others endorse thoughts of self-harm or harm to others. As part of their informed consent process, participants will be made aware of this policy, as well as the fact that confidentiality may be broken in the case that providers see an immediate threat to the patient’s or another’s safety. Patients who participate in the optional HRV measurement component of the study may experience some mild physical discomfort or skin irritation associated with wearing the ECG monitor. The risk is minimal, as this process is identical to standard ECG measurements obtained for clinical purposes, of which all participants will have undergone. No significant physical risks are expected to arise from the study. The primary risk to participants will be concerns about confidentiality, and stress of discussing the topic of their or their child’s cancer/tumor experience. While the potential risks to participants are low, we will take steps to ensure that all potential risks are handled appropriately as described

below. Due to the nature of the PRISM intervention, all staff and participants will be unblinded from the time of randomization.

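### The safety-monitoring sections give conflicting statements on stopping rules, and the planned interim does not commit to showing the DSMC distress data by arm

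*Combined protocol and SAP*

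**What the plan says.** Three statements in section 13.6 of the combined protocol and SAP deal with stopping.

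- 13.6.3 (monitoring study safety): "This study will not have pre-set stopping rules, but the DSMC will have the option of requesting the data be unblinded". It goes on to allow the committee to consider altering the study or stopping it early.
- 13.6.7 (interim analysis plan): "The DSMC will determine a priori stopping occurrence of serious events". The same sentence counts an efficacy stop after a significant interim among these.
- 13.6.7, at its end: "There are no pre-planned stopping rules for adverse events since these are not anticipated".

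On risk, section 15 says "The topics to be covered may provoke sadness, anxiety, depression, fear or doubt for AYAs and/or their parents" and adds "The primary risk to participants will be concerns about confidentiality, and stress of discussing the topic of their or their child’s cancer/tumor experience". Section 13.3 repeats the list of possible reactions and makes study-related safety concerns reportable as adverse events to the IRB and DSMC within one week. Section 13.6.3 says safety monitoring will concentrate on distress that is significant or unexpected.

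On what the DSMC sees, 13.6.3 gives it questionnaire data for all participants together, not by group. Section 13.6.7 describes an interim on the primary endpoint, for safety and missingness, at half of the target sample. Unblinded results are mentioned only for the efficacy endpoint, if an effect is found.

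The one sentence that obliges the committee to act is in 13.6.4: "The DSMC will modify or stop the study if any such complaints represent a legitimate concern about the study procedures or methods".

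**The concern.** A DSMC member reading section 13.6 cannot tell whether stopping criteria for serious events exist, are still to be written, or have been ruled out. The reason offered for having no adverse-event rule is that none are anticipated. Yet the protocol names emotional distress as a possible consequence of the topics covered and makes it the focus of monitoring. The interim has a stated safety purpose but no stated safety output: HADS is not mentioned, and a by-arm display is tied to the efficacy endpoint.

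At stake is whether a moderate, non-emergency rise in anxiety or depression in the PRISM-AC arm would be seen while the trial is running. PRISM-AC adds a new advance-care-planning session to the existing program, so this is a reasonable thing to be able to look for.

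**Working it through.** **1. The passages side by side.**

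| Question | Text A | Text B |
|---|---|---|
| Are stopping rules set in advance? | 13.6.3: no | 13.6.7: the DSMC sets them a priori for serious events, and efficacy is included |
| Are there rules for adverse events? | 13.6.7, last sentence: none | 13.6.7, earlier: a priori stopping for serious events |
| Is emotional harm foreseen? | 13.6.7: adverse events not anticipated | 13.3 and 15: may occur; 13.6.3: the focus of monitoring |
| What does the DSMC see by arm? | 13.6.3: questionnaires pooled, unblinding on request | 13.6.7: unblinded only for the efficacy endpoint, if an effect is found |

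The first two rows are contradictions. The third is a rationale at odds with the risk section. The fourth is a gap: no text commits to by-arm distress data.

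**2. What reaches the DSMC anyway.** Safety concerns go to it as adverse events within a week (13.3). Adverse-event information is collected at every assessment and sent to the chair (13.6.4). The chair may convene the committee at any time (13.6.3). The 72-hour survey review looks for missing items and immediate threats (13.3). HADS caseness is defined as 8 or more per subscale (9.6.1.1.2), but no DSMC review is linked to it.

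**3. Reproducing the plan's HADS figures.** Inputs from Table 7: SD 3.4 (HADS-A) and 3.6 (HADS-D), detectable differences 1.6 and 1.7, 72 per arm. Type I error is 5%, taken as two-sided because that reproduces the plan. SE = SD × √(2/n); power = Φ(δ/SE − 1.96).

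- HADS-A: SE = 3.4 × √(2/72) = 0.567; 1.6/0.567 = 2.82; power 0.81.
- HADS-D: SE = 3.6 × √(2/72) = 0.600; 1.7/0.600 = 2.83; power 0.81.

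The t-test version gives 0.80 for both, so the plan's 80% reproduces.

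**4. Effect of pooling.** With 1:1 allocation and equal follow-up, the pooled mean change is (change on PRISM-AC + change on usual care)/2. If only PRISM-AC worsens:

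- HADS-A worse by 1.8 (top of the MCID range in Table 7, 1.3 to 1.8): pooled 1.8/2 = 0.9.
- HADS-D worse by 1.5 (its MCID): pooled 1.5/2 = 0.75.

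Both fall below the smallest difference Table 7 calls important. An improvement on usual care would shrink them further, and a pooled drift cannot be separated from the course of advanced disease.

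**5. What a by-arm table could show at the interim.** Half of 144 is 72, or 36 per arm.

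- HADS-A: SE = 3.4 × √(2/36) = 0.80; 95% half-width 1.96 × 0.80 = 1.6 points.
- HADS-D: SE = 3.6 × √(2/36) = 0.85; 95% half-width 1.96 × 0.85 = 1.7 points.

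At two-sided 0.05, power for the Table 7 differences is about 50%; 80% power needs about 2.3 and 2.4 points (t-test). These ignore any gain from baseline adjustment.

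**6. When the interim falls.** Section 4.1 plans 78 AYAs per 12 months, or 6.5 per month, with 26% attrition. 72/0.74 = 97.3 randomized; 97.3/6.5 = 15.0 months; plus 3 months of follow-up = month 18. By then 18 × 6.5 = 117 of 195 (60%) are randomized, about 58 of them to PRISM-AC. Steady accrual is assumed.

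**The case against.** The strongest reply is that oversight of distress is real and the fault is one of drafting. That is largely right. Sections 13.3 and 13.6.4 are rules that bring individual cases to the committee. Section 13.6.3 lists adverse events among its topics, lets it request unblinding, and lets it consider stopping for harm after a very surprising result. For a low-risk supportive intervention, discretion without numerical boundaries is a defensible choice.

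Several stronger readings are therefore tempting but unsupported.

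- A reader might infer that worsening distress prompts no DSMC action. The reporting routes above say otherwise; what is missing is an obligation to review it.
- A reader might infer that the interim acts only when PRISM-AC looks better. The condition that an effect be found carries no direction, and the clause on serious events is expressly not limited to efficacy.
- A reader might infer that the chance of any rule firing on harm is nil. The DSMC is to set criteria for serious events, so their content is unstated, not zero.
- A reader might call distress an expected harm. Section 15 calls it possible and the risks low.
- A reader might think the run-in lies outside oversight. Section 13 does not exclude it; it simply does not say whether run-in questionnaire data go to the DSMC.
- The complaints sentence in 13.6.4 follows directly on adverse-event reporting and may be meant to cover adverse events.

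A practical objection also stands: section 9.2.1 blinds the analysing biostatisticians to allocation, so a by-arm display needs someone else to hold the key.

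None of this removes the contradiction within 13.6.7 and between it and 13.6.3. Nor does discretion exercised over pooled scores do the work of a by-arm display.

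**Conclusion.** The point holds as an internal contradiction with one practical consequence. The documents both deny and promise advance stopping criteria, and they justify having no adverse-event rule by a statement that their own risk and monitoring sections do not bear out. Because questionnaire data are pooled and by-arm results are promised only for efficacy, a worsening confined to PRISM-AC would appear at half its size: 0.9 for a true 1.8 on HADS-A, 0.75 for a true 1.5 on HADS-D. It could be missed unless the committee chose to ask for unblinding.

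The halving rests on 1:1 allocation, equal follow-up and no change on usual care. The by-arm precision at the interim (about ±1.6 and ±1.7 points) rests on 36 evaluable per arm and the Table 7 SDs. That is enough to show a large worsening, not to exclude a modest one. Sample size and the primary analysis are unaffected.

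**What to change.** 1. Reconcile sections 13.6.3, 13.6.7 and 15 so that a single statement on stopping and safety rules stands, covering efficacy, serious events and adverse events. Remove or correct the rationale that adverse events are not anticipated.
2. At the interim already planned, give the DSMC HADS-A, HADS-D and adverse events by arm, whatever direction they point. Have a statistician independent of the study hold the arm key, so that the blinding in 9.2.1 is kept. Section 11.4.1 already uses an independent statistician for the randomization list.
3. State in 13.6.4 whether the sentence on complaints covers adverse events.
4. State whether DSMC review covers the run-in data. Table 5 and section 9.3.1 show that HADS is collected there at baseline, week 6 and week 12.

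Whether any level of distress should prompt review, and what should follow, is for the sponsor and the DSMC to decide; no threshold is proposed here. The cost is protocol wording and one closed-report table from data already collected, with no added patients, visits or committee.
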